6.3.4.2 Day 2, Cycle 1 Continuation of Hospitalization (Cohorts 4, 5, 6)

On Day 2 of Cycle 1 of Cohort 4 and all subsequent dose escalation cohorts, the procedures listed below will be performed.

- 12-lead ECG between 14 and 16 hours after starting the infusion on Day 1;
- plasma PK samples at 14 hours, 15 hours and 16 hours after starting the infusion on Day 1;
- suspend infusion 16 hours after starting on Day 1 (immediately after drawing 16 hour PK sample), in the morning of Day 2;
- plasma PK samples at 0.5, 1, 2, 4 and 8 hours after discontinuing the infusion;
- restart infusion 8 hours later, immediately after collecting the 8-hour plasma PK sample, in the late afternoon; infusion will then be continuous until Day 8;
- clinical laboratory tests (hematology, clinical chemistries, coagulation, urinalysis);
- 12-lead ECG;
- vital signs;
- symptom-driven physical examination;
- concomitant medication assessment;
- adverse event assessment.

6.3.4.3 Day 3, Cycle 1 Continuation of Hospitalization (Cohorts 4, 5, 6)

On Day 3 of Cycle 1 of Cycle 4 and all subsequent dose escalation cohorts, the procedures listed below will be performed:

- continuous infusion via a central venous catheter of study drug;
- vital signs;
- pharmacodynamic samples (one set of samples on Day 3 or Day 4);
- symptom-driven physical examination;
- concomitant medication assessment;
- adverse event assessment.

6.3.4.4 Day 4, Cycle 1 Discharge from Hospital (Cohorts 4, 5, 6)

On Day 4 of Cycle 1 of Cohort 4 and all subsequent dose escalation cohorts, the procedures listed below will be performed prior to discharge from the hospital:

- continuous infusion via a central venous catheter of study drug;
- vital signs;
- pharmacodynamic samples (one set of samples on Day 3 or Day 4);
- symptom-driven physical examination;
- concomitant medication assessment;
- adverse event assessment.

6.3.4.5 Days 5 - 7, Cycle 1 (Cohorts 4, 5, 6)

On Days 5 through 7 of Cycle 1 in Cohort 4 and all subsequent dose escalation cohorts, the continuous infusion via a central venous catheter will continue as an outpatient. If the patient experiences any problems with the infusion, the site should be contacted.

6.3.4.6 Day 8, Cycle 1, Outpatient Visit (Cohorts 4, 5, 6)

On Day 8 (+/- 2 days) of Cycle 1 in Cohort 4 and all subsequent dose escalation cohorts, the patient will return for an outpatient visit, at which time the following procedures will be performed:

- vital signs;
- weight;
- symptom-driven physical examination;
- 12-lead ECG between 1 and 3 hours prior to discontinuing the infusion;
- plasma PK samples will also be collected on the last day of the first treatment cycle (C1D8) at three time-points separated by approximately 1 hour, with the last of these collected immediately before stopping the infusion;
- pharmacodynamic samples immediately prior to discontinuing the infusions;
- discontinuation of infusion at in the morning;
- plasma PK samples at 0.5, 1, 2, 4 and 8 hours after discontinuing the infusion;
- clinical laboratory tests (hematology, clinical chemistries, coagulation, urinalysis);
- concomitant medication check;
- adverse event assessment.

6.3.4.7 Day 15, Cycle 1, Outpatient Visit (Cohorts 4, 5, 6)

On Day 15 (+/- 2 days) of Cycle 1 of dose escalation Cohort 4 and all subsequent dose escalation cohorts, the procedures listed below will be performed during an outpatient visit:

- vital signs;
- weight;
- symptom-driven physical examination;
- clinical laboratory tests (hematology, clinical chemistries, coagulation);
- concomitant medication check;
- adverse event assessment.

6.3.4.8 Day 22, Cycle 1, Outpatient Visit for those Patients not Continuing to Cycle 2 (Cohorts 4, 5, 6)

On Day 22 (+3 days) of Cycle 1 of dose escalation Cohorts 4 and all subsequent dose escalation cohorts, the procedures listed below will be performed if the patient is not continuing to the next cycle (the procedures to be performed are the same as for an early termination/EOT visit):

- ECOG or Karnofsky/Lansky performance status;
- vital signs;
- weight;

- complete physical examination;
- 12-lead ECG;
- clinical laboratory tests (hematology, clinical chemistries, coagulation, urinalysis);
- pharmacodynamic samples;
- concomitant medication check;
- adverse event assessment.

6.3.4.9 Day 1, Cycles 2 and 3, Admission to Hospital (Cohorts 4, 5, 6)

This visit will also be considered Day 22 of the previous cycle of dose escalation Cohorts 4 and all subsequent dose escalation cohorts for those patients continuing treatment. The procedures listed below will be performed after the patient is admitted to the hospital:

- ECOG or Karnofsky/Lansky performance status;
- vital signs;
- weight;
- complete physical examination;
- 12-lead ECG;
- clinical laboratory tests (hematology, clinical chemistries, coagulation, urinalysis);
- concomitant medication check;
- adverse event assessment;
- initiation of continuous infusion via a central venous catheter.

6.3.4.10 Day 2, Cycles 2 and 3, Continuation of Hospitalization (Cohorts 4, 5, 6)

On Day 2 of Cycle 2 and 3 of dose escalation Cohort 4 and all subsequent dose escalation cohorts, the procedures listed below will be performed:

- continuous infusion via a central venous catheter of study drug;
- vital signs
- symptom-driven physical examination;
- 12-lead ECG between 20 and 24 hours of the initiation of the infusion;
- plasma PK samples between 20 and 24 hours of the initiation of the infusion;
- concomitant medication check;
- adverse event assessment.

6.3.4.11 Day 3, Cycle 2 and 3, Discharge from Hospital (Cohorts 4, 5, 6)

On Day 3 of Cycle 2 and 3 of dose escalation Cohort 4 and all subsequent dose escalation cohorts, prior to discharge from the hospital, the procedures listed below will be performed:

- continuous infusion via central venous catheter of study drug;
- vital signs
- symptom-driven physical examination;

- clinical laboratory tests (hematology, clinical chemistries, coagulation, urinalysis);
- concomitant medication check;
- adverse event assessment.

6.3.4.12 Days 4 – 7, Cycles 2 and 3 (Cohorts 4, 5, 6)

On Days 4 through 7 of Cycle 2 and 3 of dose escalation Cohort 4 and all subsequent dose escalation cohorts, the continuous infusion via a central venous catheter will continue as an outpatient. If the patient experiences any problems with the infusion, the site should be contacted.

6.3.4.13 Day 8, Cycles 2 and 3, Outpatient Visit (Cohorts 4, 5, 6)

On Day 8 (+/- 2 days) of Cycle 2 and 3 of dose escalation Cohort 4 and all subsequent dose escalation cohorts, the patient will return for an outpatient visit, at which time the infusion will be discontinued and the following procedures will be performed:

- vital signs;
- weight;
- symptom-driven physical examination;
- 12-lead ECG;
- clinical laboratory tests (hematology, clinical chemistries, coagulation, urinalysis);
- concomitant medication check;
- adverse event assessment.

6.3.4.14 Day 15, Cycles 2 and 3, Outpatient Visit (Cohorts 4, 5, 6)

On Day 15 (+/- 2 days) of Cycle 2 and 3 of dose escalation Cohort 4 and subsequent dose escalation cohorts, the procedures listed below will be performed during an outpatient visit:

- clinical laboratory tests (hematology, clinical chemistries, coagulation);
- concomitant medication check;
- adverse event assessment.

6.3.4.15 Day 22, Cycles 2 and 3, Outpatient Visit (Cohorts 4, 5, 6)

On Day 22 (+/- 3 days) of Cycle 2 and 3 of dose escalation Cohort 4 and all subsequent dose escalation cohorts, the procedures listed below will be performed during an outpatient visit, if the patient is not continuing to the next cycle (the procedures to be performed are the same as for an early termination/EOT visit:

- ECOG or Karnofsky/Lansky performance status;
- weight;
- complete physical examination;
- 12-lead ECG;
- clinical laboratory tests (hematology, clinical chemistries, coagulation, urinalysis);
- a CT scan or MRI will be done every 6 weeks during the study (end of Cycles 2, 4, 6, etc.). The same method of assessing disease must be used throughout the study;

- concomitant medication check;
- adverse event assessment.

6.3.4.16 Day 1, Cycle 4 and all Subsequent Dose Escalation Cycles, Outpatient Visit (Cohorts 4, 5, 6)

This visit will also be considered Day 22 of the previous cycle of dose escalation Cohort 4 and all subsequent dose escalation cohorts for those patients continuing treatment. The procedures listed below will be performed:

- ECOG or Karnofsky/Lansky performance status;
- vital signs;
- weight;
- complete physical examination;
- 12-lead ECG;
- clinical laboratory tests (hematology, clinical chemistries, coagulation, urinalysis);
- a CT scan or MRI will be done every 6 weeks during the study (end of Cycles 2, 4, 6, etc.). The same method of assessing disease must be used throughout the study;
- concomitant medication check;
- adverse event assessment;
- initiation of continuous infusion via a central venous catheter; infusion will continue until Day 8.

6.3.4.17 Days 2 – 7, Cycle 4 and all Subsequent Dose Escalation Cycles (Cohorts 4, 5, 6)

On Days 2 through 7 of Cycle 4 and all subsequent cycles of dose escalation Cohort 4 and all subsequent dose escalation cohorts, the continuous infusion via a central venous catheter will continue as an outpatient. If the patient experiences any problems with the infusion, the site should be contacted.

6.3.4.18 Day 8, Cycle 4 and all Subsequent Dose Escalation Cycles, Outpatient Visit (Cohorts 4, 5, 6)

On Day 8 (+/- 2 days) of Cycle 4 and all subsequent cycles of dose escalation Cohort 4 and all subsequent dose escalation cohorts, the patient will return for an outpatient visit, at which time the infusion will be discontinued and the following procedures will be performed:

- vital signs;
- weight;
- symptom-driven physical examination;
- 12-lead ECG;
- clinical laboratory tests (hematology, clinical chemistries, coagulation, urinalysis);
- concomitant medication check;
- adverse event assessment.

6.3.4.19 Day 22, Cycle 4 and all Subsequent Dose Escalation Cycles, Outpatient Visit (Cohorts 4, 5, 6)

On Day 22 (+/- 3 days) of Cycle 4 and all subsequent cycles of dose escalation Cohort 4 and all subsequent dose escalation cohorts, the procedures listed below will be performed if the patient is not continuing to the next cycle (the procedures to be performed are the same as for an early termination/EOT visit):

- ECOG or Karnofsky/Lansky performance status;
- vital signs;
- weight;
- complete physical examination;
- 12-lead ECG;
- clinical laboratory tests (hematology, clinical chemistries, coagulation, urinalysis);
- a CT scan or MRI will be done every 6 weeks during the study (end of Cycles 2, 4, 6, etc.). The same method of assessing disease must be used throughout the study;
- concomitant medication check;
- adverse event assessment.

6.3.5 All Schedule Escalation Cohorts and Cycles (Cohorts 7, 8, 9)

No hospitalization is required for the schedule escalation cohorts.

6.3.5.1 Day 1, All Schedule Escalation Cohorts and Cycles (Cohorts 7, 8, 9)

On Day 1 of Cycle 1 for all schedule escalation cohorts, the following procedures will be performed.

- ECOG or Karnofsky/Lansky performance status**;
- Weight**; height Cycle 1 only
- vital signs;
- 12-lead ECG: pre-dose**; For Cycle 1 only, post-dose between 1 and 3 hours after initiation of infusion;
- clinical laboratory tests (hematology, clinical chemistries, coagulation, urinalysis)**;
- for Cycle 1 only, urine pregnancy test (women of childbearing potential only)**;
- complete physical examination**;
- for Cycles 1 and 2 only, pharmacodynamic samples: pre-dose on Day 1; Samples in subsequent cycles may be collected if clinically indicated, for example, to evaluate biomarkers of response
- a single pharmacokinetic sample (see section 6.3.9);
- a single sample for pharmacogenomics to assess CYP polymorphisms
- the TK216 infusion via a central venous catheter will be initiated; infusion will continue for the number of days assigned in the cohort;
- the vincristine infusion will be administered prior to the start of the TK216 infusion starting in cycle 3+ of schedule escalation cohorts, if applicable;
- the vincristine infusion will be administered prior to the start of the TK216 infusion starting in cycle 1 of expansion cohort, if applicable;

- concomitant medication assessment;
- adverse event assessment.

** If the assessments for ECOG or Karnofsky/Lansky performance status, weight, physical examination, ECG, clinical laboratory tests and urine pregnancy test were performed within approximately 72 hours prior to starting a new infusion cycle, these assessments do not need to be repeated.

6.3.5.2 Day 4 (+/-1), All Schedule Escalation Cohorts and Cycles (Cohorts 7, 8, 9)

On Day 4 of Cycle 1, the procedures listed below will be performed.

- continuous infusion via a central venous catheter of study drug;
- For Cycle 1 only, pharmacodynamic sample;
- a single pharmacokinetic sample (see section 6.3.9) if the patient is in the schedule escalation segment;

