- plasma PK samples will also be collected on the last day of the first treatment cycle (C1D8) at three time-points prior to discontinuing the infusion, separated by approximately 1 hour, with the last of these collected immediately before stopping the infusion;
- discontinuation of infusion at in the morning;
- plasma PK samples at 0.5, 1, 2, 4 and 8 hours after discontinuing the infusion;
- vital signs;
- weight;
- symptom-driven physical examination;
- 12-lead ECG;
- clinical laboratory tests (hematology, clinical chemistries, coagulation, urinalysis);
- concomitant medication check;
- adverse event assessment.

4.2.2.9 **Day 15, Cycle 1 assessments, Outpatient Visit (Cohorts 1, 2, 3)**

On Day 15 (+/- 2 days) of Cycle 1 of dose escalation Cohorts 1, 2 and 3, the procedures listed below will be performed during an outpatient visit:

- vital signs;
- weight;
- symptom-driven physical examination;
- clinical laboratory tests (hematology, clinical chemistries, coagulation);
- concomitant medication check;
- adverse event assessment.

4.2.2.10 **Day 22, Cycle 1 assessments, Outpatient Visit for Patients not Continuing Treatment (Cohorts 1, 2, 3)**

On Day 22 (+3 days) of Cycle 1 of dose escalation Cohorts 1, 2 and 3, the procedures listed below will be performed during an outpatient visit, if the patient is not continuing to Cycle 2 (the procedures to be performed are the same as for an early termination visit/End of Treatment visit, but the patient will be considered to have completed the study if the patient completes Cycle 1):

- ECOG or Karnofsky/Lansky performance status;
- vital signs;
- weight;
- complete physical examination;

- 12-lead ECG;
- clinical laboratory tests (hematology, clinical chemistries, coagulation, urinalysis);
- pharmacodynamic samples;
- concomitant medication check;
- adverse event assessment.

4.2.2.11 Day 1 of Cycle 2 and 3, Admission to Hospital (Cohorts 1, 2, 3)

This visit will also be considered Day 22 of the previous cycle of dose escalation Cohorts 1, 2 and 3 for those patients continuing treatment. The procedures listed below will be performed prior to the start of the infusion:

- ECOG or Karnofsky/Lansky performance status;
- vital signs;
- weight;
- complete physical examination;
- 12-lead ECG pre-dose;
- clinical laboratory tests (hematology, clinical chemistries, coagulation, urinalysis);
- pharmacodynamic samples;
- concomitant medication check;
- adverse event assessment;

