- adverse event assessment.

4.2.2.17 **Day 22 of Cycle 2 and 3, Outpatient Visit (Cohorts 1, 2, 3)**

On Day 22 (+/- 3 days) of Cycles 2 and 3 of dose escalation Cohorts 1, 2 and 3, the procedures listed below will be performed during an outpatient visit, if the patient is not continuing to the next cycle (the procedures to be performed are the same as for an early termination/EOT visit:

- ECOG or Karnofsky/Lansky performance status;
- weight;
- complete physical examination;
- 12-lead ECG;
- clinical laboratory tests (hematology, clinical chemistries, coagulation, urinalysis);

- a CT scan or MRI will be done every 6 weeks during the study (end of Cycles 2, 4, 6, etc.). The same method of assessing disease must be used throughout the study;
- concomitant medication check;
- adverse event assessment.

4.2.2.18 **Day 1, Cycle 4 and all Subsequent Cycles, Outpatient Visit (Cohorts 1, 2, 3)**

This visit will also be considered Day 22 (+/- 3 days) of the previous cycle of dose escalation Cohorts 1, 2 and 3 for those patients continuing treatment. The procedures listed below will be performed:

- ECOG or Karnofsky/Lansky performance status;
- vital signs;
- weight;
- complete physical examination;
- 12-lead ECG;
- clinical laboratory tests (hematology, clinical chemistries, coagulation, urinalysis);
- a CT scan or MRI will be done every 6 weeks during the study (end of Cycles 2, 4, 6, etc.). The same method of assessing disease must be used throughout the study;
- concomitant medication check;
- adverse event assessment;
- initiation of continuous infusion via a central venous catheter; infusion will continue until Day 8.

4.2.2.19 **Days 2 – 7, Cycle 4 and all Subsequent Cycles (Cohorts 1, 2, 3)**

On Days 2 through 7 of Cycle 4 and all subsequent cycles, the continuous infusion via a central venous catheter will continue as an outpatient. If the patient experiences any problems with the infusion, the site should be contacted.

4.2.2.20 **Day 8, Cycle 4 and all Subsequent Cycles, Outpatient Visit (Cohorts 1, 2, 3)**

On Day 8 (+/- 2 days) of Cycle 4 and all subsequent cycles of dose escalation Cohorts 1, 2 and 3, the patient will return for an outpatient visit, at which time the infusion will be discontinued and the following procedures will be performed:

- vital signs;
- weight;
- symptom-driven physical examination;
- 12-lead ECG;
- clinical laboratory tests (hematology, clinical chemistries, coagulation, urinalysis);
- concomitant medication check;

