6.3.6 Expansion Cohort (Cohort 10)

4.2.3.1 Expansion Cohort: On study Schedule (Cohort 10)

Patients enrolled in the Expansion Cohort will be assessed and treated the same as described for the Schedule Escalation Cohorts in Section 6.3.5, as applicable to the selected regimen.

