4.2.3.2 Early Termination/End of Treatment Visit, All Cohorts, All Cycles (Cohort 10)

The following procedures will be performed at the time a patient is discontinued from the study, if prior to completing a cycle. This visit should be performed within 2 days of discontinuation. The End of Treatment Visit will be done if a patient completes a cycle but does not continue to the next cycle. This visit should be performed either at the last visit in the cycle (Day 22) or within 7 days after the completion of the cycle. During the schedule escalation segment, this visit should be done within 2 days if the patient discontinues before the end of cycle 1 or if the patient discontinues during an infusion of any subsequent cycle, or within 7 days if the patient discontinues after the end of an infusion but prior to starting the next cycle.

- ECOG or Karnofsky/Lansky performance status
- vital signs;
- weight;
- complete physical examination;
- 12-lead ECG;
- clinical laboratory tests (hematology, clinical chemistries, coagulation, urinalysis);
- urine pregnancy test: women of child-bearing potential only;
- if a CT scan or MRI is due, it should be done at this visit. The same method of assessing disease must be used throughout the study;
- concomitant medication check;
- adverse event assessment.

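### In the narrative visit lists, Cohorts 1-10 have no pregnancy test on Day 1 of any cycle after the first, although Part 4 tests every cycle; in Part 2 vincristine may first be given at least about 34 days after the last listed test (low priority)

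*Combined protocol and SAP*

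**What the plan says.** **Cohorts 7-9.** Section 6.3.5.1 is headed as Day 1 for all cycles, and it carries an instruction for vincristine from Cycle 3 onward. Its pregnancy test item reads "for Cycle 1 only, urine pregnancy test (women of childbearing potential only". Its footnote waives a repeat on Day 1 if items including "clinical laboratory tests and urine pregnancy test were performed within approximately 72 hours prior to starting a new infusion cycle". The later visits in Sections 6.3.5.2 to 6.3.5.8 list no pregnancy test.

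**Cohort 10.** Section 4.2.3.1 states: "Patients enrolled in the Expansion Cohort will be assessed and treated the same as described for the Schedule Escalation Cohorts in Section 6.3.5".

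**Cohorts 1-6.** The test is listed on Cycle 1 Day 1 (Sections 4.2.2.1 and 6.3.4.1). It is absent from the four Day 1 lists for later cycles:
- "Day 1 of Cycle 2 and 3, Admission to Hospital (Cohorts 1, 2, 3" (4.2.2.11)
- "Day 1, Cycle 4 and all Subsequent Cycles, Outpatient Visit (Cohorts 1, 2, 3" (4.2.2.18)
- "Day 1, Cycles 2 and 3, Admission to Hospital (Cohorts 4, 5, 6" (6.3.4.9)
- "Day 1, Cycle 4 and all Subsequent Dose Escalation Cycles, Outpatient Visit (Cohorts 4, 5, 6" (6.3.4.16)

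**End of treatment.** Section 4.2.3.2 lists "urine pregnancy test: women of child-bearing potential only".

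**Part 4.** Section 4.2.4.1 puts a pregnancy test on Day 1 under an all-cycles heading, with no cycle limit. Section 4.2.4.5 adds one when Day 28 is also Day 1 of the next cycle.

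**Vincristine.** Section 2.3 allows it in Part 2 once Cycle 2 is complete. Section 7.3.5.1 records fetal toxicity and teratogenicity in humans.

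**The concern.** The protocol treats fetal exposure as a real hazard. It requires two contraceptive methods and documented understanding of TK216's possible teratogenicity (Section 3.1, criteria 15 and 17). Even so, for ten of the eleven cohorts the lists give no scheduled way to detect a contraceptive failure while treatment continues. In Part 2 a second drug with known human teratogenicity may be added inside that interval without a new test.

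The rule on reporting a pregnancy (Section 4.1.7.6) and the option to withdraw a patient for it (Section 4.2.8) can act only once the pregnancy is known. Until then, detection depends on the patient's report or an unscheduled test. The interval lasts as long as treatment does, which Section 2 caps at two years.

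No endpoint, analysis or dose decision is involved. This is a participant-safety and consistency point.

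**Working it through.** The protocol gives no figure to reproduce. The check is a reading of every narrative visit list, followed by simple addition.

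**1. Where a pregnancy test is listed**

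| Cohorts | Screening | Cycle 1 Day 1 | Day 1 of later cycles | At stopping |
|---|---|---|---|---|
| 1-3 | yes (4.2.1) | yes (4.2.2.1) | no (4.2.2.11, 4.2.2.18) | unclear |
| 4-6 | yes (4.2.1) | yes (6.3.4.1) | no (6.3.4.9, 6.3.4.16) | unclear |
| 7-9 | yes (4.2.1) | yes (6.3.5.1) | no, by express limit (6.3.5.1) | yes, if 4.2.3.2 covers all cohorts |
| 10 | yes (4.2.1) | yes (via 4.2.3.1) | no (via 4.2.3.1) | yes (4.2.3.2) |
| 11 | not compared | yes (4.2.4.1) | yes (4.2.4.1, 4.2.4.5) | yes (4.2.5) |

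**2. Why stopping is unclear in Cohorts 1-6.** Six Day 22 lists cover patients who do not continue: 4.2.2.10, 4.2.2.17, 4.2.2.21, 6.3.4.8, 6.3.4.15 and 6.3.4.19. Each says that its procedures match the early termination or end-of-treatment visit, and none includes the pregnancy test that Section 4.2.3.2 lists. The heading of 4.2.3.2 also names both all cohorts and Cohort 10.

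**3. Part 2: days from the Cycle 1 Day 1 test to the earliest vincristine dose.** Inputs:
- Infusion length L: 10 days in the first cohort, and 14 days in the Section 2.3 illustration of the next step. Lengthening is allowed only from Cycle 3, so L is the same in Cycles 1 and 2.
- Rest after Cycle 1: 14 days, required by Section 2.3.
- Rest after Cycle 2: r. Section 2.3 lets it be reduced, and Section 6.3.5.8 foresees a new cycle starting before its seven-day visit. I take r = 0 as the assumed minimum and r = 14 as the assumed unreduced case.

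Cycle 3 Day 1 falls L + 14 + L + r days after Cycle 1 Day 1.

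| L | r = 0 | r = 7 | r = 14 |
|---|---|---|---|
| 10 | 10 + 14 + 10 = 34 | 41 | 48 |
| 14 | 14 + 14 + 14 = 42 | 49 | 56 |

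Against the 28-day interval between Part 4 tests (no treatment rests), the range runs from 34/28 = 1.21 to 56/28 = 2.00. Using the 72-hour allowance for the Cycle 1 test can add up to about 3 days. Section 6.3.5.8 also lets its seven-day visit count as Day 1 of Cycle 2. That sits awkwardly with the 14-day rest stated there and in Section 2.3. If a site followed it, each figure would be 7 days shorter (minima 34 - 7 = 27 and 42 - 7 = 35).

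**4. Part 1 (21-day cycles).** Later cycles start at weeks 3, 6, 9 and so on. A patient who stops at the 6-week scan has had one cycle start without a listed test (week 3). One who stops at 12 weeks has had three (weeks 3, 6 and 9).

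**The case against.** **The governing schedule may list the test.** Sections 2.3 and 2.4 cite a Schedule of Events in Section 16.3, and Section 4.2.8 cites a flow chart. Neither is in the supplied text. A reader might infer that women in Cohorts 1-10 went untested during treatment; the documents do not support that, because a per-cycle test in the unseen schedule cannot be excluded. What stands is narrower. If Section 16.3 has such a test, it conflicts with the Cycle 1 limit in 6.3.5.1, so the text needs correcting either way.

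**Other text points to more testing.** Section 4.1.6.1 says that urine tests will be done in females of childbearing potential but gives no timing. The 6.3.5.1 footnote mentions the test in connection with a new cycle, but it only waives repeats. Neither schedules a test on treatment.

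**Risk is already controlled.** A negative test within 7 days of starting treatment (criterion 13), contraception and documented counselling lower the chance of an exposed pregnancy. They do not detect a failure.

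**Cohorts 1-10 may be finished.** Section 4.2.4 gives the Cohort 11 regimen as the one in use from version 7.0. Section 2 fixes Part 2 at three cohorts (7-9), although Section 2.3 still anticipates 4 to 6. This suggests, without proving, that escalation had ended. It is the weightiest objection and is why the priority is low.

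**The gap is modest and optional.** The 34-day minimum exceeds the Part 4 interval by only 6 days, Part 4 intervals also lengthen with rests, and vincristine in Part 2 is not mandatory. All of that is fair.

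**Conclusion.** The point holds as a statement about the narrative visit lists. Cohorts 7-10 are limited to a Cycle 1 test by express wording, Cohorts 1-6 list none on Day 1 of Cycle 2 onward, and Part 4 tests every cycle with the same investigational drug. In Part 2 the first vincristine dose can fall at least about 34 or 42 days after the last listed test, assuming the required 14-day rest after Cycle 1 and no rest after Cycle 2.

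Two further readings go too far. A reader might extend the vincristine point to Part 3, but vincristine starts there in Cycle 1, so the Cycle 1 test covers the first dose and only later doses lack one. A reader might also take the end-of-treatment test as assured for all ten cohorts; for Cohorts 1-6 the lists contradict each other.

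The number of women of childbearing potential is not given, so the number exposed to the gap cannot be estimated. This is a cheap improvement of low priority.

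**What to change.** 1. **Section 6.3.5.1:** delete the Cycle 1 restriction on the pregnancy test and require a negative result before that cycle's infusion starts, including before the first vincristine dose. The 72-hour footnote can stay. Cohort 10 follows through Section 4.2.3.1.
2. **Cohorts 1-6, for any patient still on treatment:** add a urine pregnancy test for women of childbearing potential to the later-cycle Day 1 lists (4.2.2.11, 4.2.2.18, 6.3.4.9, 6.3.4.16) and to the six Day 22 lists for patients who stop (4.2.2.10, 4.2.2.17, 4.2.2.21, 6.3.4.8, 6.3.4.15, 6.3.4.19).
3. **Section 16.3:** check its schedule and make the lists and the table agree. If it already has a test each cycle, the change is to the narrative only.

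The running cost is one urine test per cycle for women of childbearing potential. The Day 1 visits already collect urine for urinalysis, so no new visit or sample is needed. The benefit is confined to patients still treated or enrolled in Cohorts 1-10. If the sponsor confirms that there are none, the edits have no practical effect.
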